If the technology's intended use is to support the recording of data in patients' electronic health record, which informs future clinical decision and management, it could fall into Tier C: informing clinical decisions. This would be the case particularly if there are high risks associated with the algorithm not performing as expected (such as potential danger to patients). However, this is not the case with MiADE; the system itself merely suggests structured data for information that is already in the health record in a free text form.

6.2 Storage and handling of drugs at site (if applicable)

Not applicable for this study.

6.3 Accountability of drug (if applicable)

Not applicable for this study.

6.4 Concomitant medication (if applicable)

Not applicable for this study.

6.5 Dosages, modifications, and methods of administration (if applicable)

Not applicable for this study.

7. TRIAL PROCEDURES

7.1 Pre-intervention assessments

There are no trial specific procedures to be carried out after consent to assess patient or clinician eligibility.

7.2 Registration/Randomisation Procedures (delete as appropriate) (if applicable)

Clinician participant registration will be undertaken centrally by the coordinating trial team. Clinician login names for the electronic health record system will be recorded on the study database within the UCLH system. For patients for observed consultations, the clinic code of the clinic they attend

and the time and date of their appointment will be recorded on the study database. All data will be stored on UCLH servers.

There are no randomisation procedures as this is a single-arm intervention study with before and after comparison.

7.3 Baseline and Intervention Procedures

7.3.1 Baseline data

Clinician participants: A baseline questionnaire will be administered to gather information about specialty, seniority, and self-rated level of expertise with the electronic health record system.

Patient participants: All data on patients will be collected as part of the interview after the observed consultation. This will include questions on patient characteristics including age group, gender and ethnicity. This information will be collected to ensure the diversity of the patient sample.

7.3.2 Intervention Procedures

Clinician participants: Clinicians will be consented and asked to watch a training video on the need for structured data recording and how to use the MiADE system. They will then be asked to fill in a pre-MiADE questionnaire survey on their experience of using the electronic health record system.

Clinicians in the qualitative substudy will be observed for at least 4 face to face consultations (2 before MiADE and 2 after) for which patients have given consent. They will also be interviewed after using MiADE. The time period between consent and having the MiADE system switched on will be at least 4 weeks. Patient participants in the qualitative substudy will be consented prior to their consultation and the researcher will sit in the consultation to observe the interactions between doctor, patient and the computer. A purposive sample of 5 clinicians (covering a range of inpatient teams and levels of seniority) from the inpatient substudy will also be interviewed post MiADE switch on, around the time of the questionnaire survey.

During the observed consultations, the researcher will make notes but no recording devices will be used. The researcher will leave the room or stay outside the curtains if the patient is being examined. After the consultation, the researcher may ask questions of the clinician in order to clarify any behaviours or events that were observed.

Patients will be invited to participate in an interview following the consultation. This may be immediately after the consultation or by telephone or virtually at a convenient time for them. Interviews will explore individuals' experience, understanding and perception of the MiADE system. The interview questions will be informed technology evaluation and behavioural change theories and developed from relevant literature and the experience of the research team. The interview schedule will mainly comprise open questions to allow patients to provide their own perspectives,

be iterated in consultation with our patient and public partners and piloted before use to ensure face validity.

We anticipate a total of 10-15 interviews for patients for each phase, although this will be subject to saturation checking. Through targeted patient recruitment we will ensure, as far as possible, that the interview sample reflects diversity with respect to gender, age, ethnicity and any other characteristics identified as important during the data collection period.

Audio data collected from patient and clinician interviews will be transferred from a passwordprotected digital recording device directly to a secure computing environment. It will then be transcribed and identifiable features removed by a member of the research team. De-identified transcripts will be used for the purposes of conducting the qualitative analysis. Anonymised quotations will be presented in the published study results.

After the MiADE system has been switched on, clinicians will be given a post-MiADE survey on their experience of using the system. Clinicians in the outpatient qualitative substudy will also be observed for at least 2 consultations post-MiADE, for which patients will be asked to consent. Clinicians should have had access to the MiADE system for at least 2 weeks before the post-MiADE survey or observation.

Patients who are under the care of a clinician participant but not part of the qualitative substudy will not experience any difference in the care they receive.

7.4 Subsequent assessments and procedures

A schedule of all trial assessments and procedures is set out in Appendix 1.

7.5 Samples (if applicable)

Not applicable for this study.

7.5.1 Laboratory assessments

Not applicable for this study.

7.5.2 Translational research samples (if applicable)

Not applicable for this study.

7.5.3 Sample storage and transfer

No samples will be collected from patients as part of this study.

7.6 Discontinuation/withdrawal of participants

In consenting to participate in the trial, patient participants are consenting to intervention, assessments, follow-up and data collection.

It is always within the remit of the physician responsible for a patient to withdraw the patient from a trial (or certain aspects of the trial) for appropriate medical reasons, adverse events or new information gained about an intervention. A participant may be withdrawn from trial whenever continued participation is no longer in the participant's best interests, but the reasons for doing so must be recorded. Reasons for discontinuing the trial may include:

- Breakdown of the doctor-patient relationship
- The topic of the consultation is particularly distressing
- Patient withdraws consent
- Patient is clinically unwell and requires emergency treatment

The decision to withdraw a participant from the trial will be recorded in the CRF and medical notes/electronic health record system. If a participant explicitly states they do not wish to contribute further data to the trial their decision must be respected and recorded in the CRF and medical notes. Any inclusion of collected data needs to be used in accordance with GDPR and HRA guidance.

7.7 Definition of End of Trial

The expected duration of the trial is 5 months from recruitment of the first participant.

The planned end of the trial is 8 weeks after the MiADE system has been switched on for the last clinician participant to enter the trial.

[figure not shown]
8. FINANCE AND SUPPLY OF EQUIPMENT

The research costs for the study have been supported by NIHR AI award (grant number AI_AWARD01864, amount £644k, awarded August 2020). This funding covers the programming and installation of the MiADE system for evaluation, researcher salaries, installation of computer hardware, consultancy fees and contingency.

9. DATA MANAGEMENT

The overall data flows for the MiADE evaluation study are illustrated in Figure 5.

Figure 5: Data flow diagram for MiADE evaluation study

Data flow legend

9.1 Confidentiality

The study is compliant with the requirements of the General Data Protection Regulation (2016/679) and the UK Data Protection Act (2018). All Investigators and study site staff will comply with the requirements of the General Data Protection Regulation (2016/679) with regards to the collection, storage, processing and disclosure of personal information, and will uphold the Act's core principles.

UCL is the data controller; the UCL Data Protection Officer is [contact]. The data processors are [name] (PI), [name] (software developer), [name] (software developer), [name] (researcher) and other members of the Trial Management Group. The study will be collecting the following personal data:

- Consent forms from patients and clinicians
- Survey responses from clinician participants, collected electronically
- Researcher notes observing consultations
- Notes, transcripts and recordings of interviews with patients and clinicians
- Patient information from patients under the care of the clinic code or under the care of an inpatient team participating in the study will be extracted for analysis of completeness of data. The extract will be pseudonymised and will contain minimal data that is required to answer the research questions.

Paper records will be stored in a secure filing cabinet. Electronic study records will be stored on UCLH servers or in the UCL data safe haven, which has been certified to the ISO27001 information security standard and conforms to NHS Digital's Information Governance Toolkit.

The Case Report Forms (CRFs) will not bear the participant's name or other personal identifiable data. For patients in the qualitative study, the patient's clinic code, appointment time and trial identification number will be used for identification and this will be clearly explained to the patient in the patient information sheet. Patient consent for this will be sought.

9.2 Data collection tools and source document identification

Data from clinician surveys will be collected electronically using a survey tool. Data from clinician and patient interviews and patient observation will be collected on trial specific case report forms. For patients in the qualitative substudy, information about diagnoses, medication and allergies in their electronic health record (whether in free text or in structured form) will be manually abstracted into an electronic database.

It is the responsibility of the investigator to ensure the accuracy of all data entered in the CRFs. The delegation log will identify all those personnel with responsibilities for data collection and handling, including those who have access to the trial database.

9.3 Completing Case Report Forms

Once completed the original CRFs must be sent to the principal investigator.

9.4 Data Handling

In the study, observations of consultations, interview responses, and medical information abstracted from their health record will be collected from patients in the qualitative substudy in accordance with the patient consent form, patient information sheet and sections 4 and 7.3.2 of this protocol.

With the consent of the patient, interviews will be audio recorded, anonymised by the researcher and then transcribed verbatim by a professional transcribing service as soon as possible after conducting the interviews.

All qualitative data will be entered into NVivo software (QSR International (UK) Limited, Southport, UK), a data management and analysis programme to enable the application of qualitative analytical procedures which employ a system of coding and memoing developed by Lofland and Lofland (1995).

For patients who are not consented to be in the qualitative substudy but are treated by clinicians in the study, pseudonymised information about the medication, allergies and diagnoses recorded in their health record will be extracted and analysed to assess the performance of the MiADE system. All data for this study will be stored and analysed on UCLH servers. UCLH will act as the data controller of such data for the study.

UCLH will process, store and dispose of patient data in accordance with all applicable legal and regulatory requirements, including the Data Protection Act 2018 and any amendments thereto.

The patient data will not be transferred to any party not identified in this protocol and are not to be processed and/or transferred other than in accordance with the patients' consent.

Direct access to the data will be granted to authorised representatives from the Sponsor, host institution and the regulatory authorities to permit study-related monitoring, audits and inspections, in line with participant consent.

Personal Data breaches

Personal data breaches will be immediately reported to the UCL Information Security Group (ISG) and the UCL Data Protection Officer ([contact]), and to the Sponsor via the UCL JRO research incident reporting form (as per form and guidance: https://www.ucl.ac.uk/legal-services/guidance/reporting-loss-personal-data). The following information will be provided: full details as to the nature of the breach, an indication as to the volume of material involved, and the sensitivity of the breach (and any timeframes that apply). Sites will additionally follow their Trust incident reporting mechanisms, and will document this within their TMF/ISFs.

10.STATISTICAL CONSIDERATIONS

10.1 Primary outcome

Study 1 (outpatient): The primary outcome is the difference in the mean number of structured problem list, medication or allergy entries, comparing the time periods with and without MiADE switched on.

Study 2 (inpatient): The primary outcome is the difference in the proportion of ICD-10 discharge diagnoses with a corresponding structured problem list entry, comparing the time periods with and without MiADE switched on.

10.2 Secondary outcome(s)

To estimate the proportion of structured data items suggested by MiADE that are accepted by the clinician for entry into the structured record.

To estimate and summarise (mean, standard deviation, median, interquartile range) the distribution of computing time required per consultation note.

Clinician and patient perceptions of structured data recording in electronic health records and the MiADE system.

10.3 Sample size calculation

Based on a prior audit [15], 62% of problem list entries were entered as structured data and there were mean 8.8 problems per patient. In order to detect an increase from 62% to 70%, 549 problems are required in each group, which is 62 patients (assuming 8.8 problems per patient). This study aims to recruit at least 5 inpatient teams who would each discharge at least one inpatient per day, giving 100 patients in a 4-week period.

For outpatients, assuming each clinician sees 5 new patients each week, they will see 20 patients in a 4 week period. Using the same calculation as for inpatients, a sample size of only 5 clinicians is required to investigate the primary endpoint. However, a larger sample (target = 25) will be used in order to assess variability between clinicians.

For the patients in the qualitative substudies, there is no technique for formal sample size estimation. The number of observed clinicians (5 for inpatients and 5 for outpatient) and number of outpatient observations pre and post MiADE (2 per clinician per phase) has been selected to have a high probability of demonstrating potential themes. Using the method of Potts et al. [17], with a sample size of 5, assuming random sampling, there is 83% probability of surfacing a theme exhibited by 70% of the population.

The maximum number of clinicians to be recruited has been set at 100 according to the specification of the NLP server intended to be used for this trial.

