Inpatient clinical teams will be recruited to the study. Within each team, the clinicians (consultants, specialty and foundation doctors who see inpatients) will be recruited, consented and trained. Doctors rotate through clinical teams every few months, so the MiADE system will be switched on for the relevant clinicians at a time point half-way through the four-month rotation, to allow comparison of the completeness of structured recording of diagnoses on the problem list before and after the switch-on. The 'gold standard' of recording of diagnoses will be the ICD-10 coded billing diagnoses which are assigned by the clinical coding team based on a review of the entire medical record after a patient is discharged. Diagnoses will be aggregated by groups of ICD-10 codes similar to a previous UCLH audit [15], and a diagnosis will be considered as included in the problem list if any SNOMED CT concept which maps to an ICD-10 code in the group was recorded on or prior to the patient's discharge date. This flexibility of mapping will be permitted as different professionals may assign different clinical codes to the same condition based on their interpretation and judgement, especially for cases where an exact code does not exist. The proportion of ICD-10 code groups with a problem list entry will be calculated per patient, and aggregated across the patients under the care of the clinical team during the study period.

For a sample of 5 clinicians, semi-structured interviews will be held with the clinicians after they have been using MiADE for at least two weeks, using the same questions as for outpatient doctors except the question on medications, as MiADE for inpatients does not handle medications.

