10.6.2 Primary outcome analysis

For the outpatient study, multilevel Poisson regression will be used to calculate the ratio of counts of structured data entries between pre-MiADE and post-MiADE, with the clinician (clinic code) as a random effect to account for clustering by clinician. This analysis will also yield an estimate of the variability of the effect by clinician.

For the inpatient study, the primary outcome will be the difference in proportion of ICD-10 coded diagnoses recorded in the problem list comparing pre-MiADE and post-MiADE. This measure will be calculated separately for each inpatient team and then summarised as an overall difference in proportions, combining data from the different teams. For the inpatient study it will not be possible to differentiate results from patients seen by different clinicians within a team.

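### The inpatient sample size converts 549 problems into 62 patients with no allowance for correlation between diagnoses in the same patient, so 62 patients do not give the implied power if that correlation is positive

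*Protocol*

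**What the plan says.** Protocol section 10.3 takes its inputs from a prior audit: "62% of problem list entries were entered as structured data and there were mean 8.8 problems per patient". To detect a rise to 70%, it concludes that "549 problems are required in each group, which is 62 patients (assuming 8.8 problems per patient". It names no significance level, power, ICC or design effect. It then expects "at least 5 inpatient teams who would each discharge at least one inpatient per day, giving 100 patients in a 4-week period". On the outpatient side it applies the same calculation and concludes that 5 clinicians, each seeing 20 new patients in 4 weeks, would be enough, although it sets a larger target.

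The Study Summary estimates 600 inpatient records, from 5 teams discharging 5 patients a week over 24 weeks.

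On the inpatient outcome, section 4 (Study 2) says: "The proportion of ICD-10 code groups with a problem list entry will be calculated per patient", with aggregation across the team's patients afterwards. Section 10.6.2 says the difference in proportion of coded diagnoses is "calculated separately for each inpatient team and then summarised as an overall difference in proportions, combining data from the different teams". In the same section the outpatient analysis has a clinician random effect for clustering. The inpatient analysis has no named allowance for clustering by patient.

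**The concern.** The two-proportion formula counts independent yes/no observations. Here the observation is whether one coded diagnosis reached the problem list, and a patient contributes 8.8 of them on average. One team keeps that patient's list during one admission. A well-kept list will tend to hold most of the diagnoses and a neglected list few, so nine diagnoses from one patient probably carry less information than nine from nine patients. Dividing the number of problems by 8.8 ignores this.

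At stake is the stated justification for the inpatient study size. A reader is told that 62 patients per period suffice and that 100 leave a comfortable margin. Whether either is true depends on a correlation that the protocol does not mention. The outpatient statement about 5 clinicians inherits the problem.

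**Working it through.** **Inputs.** From section 10.3: p1 = 0.62, p2 = 0.70, m = 8.8 diagnoses per patient, and 100 inpatients per 4 weeks. From the Study Summary: 5 teams × 5 patients × 8 weeks = 200 per 8 weeks. Assumed because the protocol does not state them: two-sided alpha 0.05, power 80%, and ICC between 0.05 and 0.3.

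**Step 1: reproduce the protocol's figure.** With the pooled proportion p = 0.66,

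n = [1.96 × √(2 × 0.66 × 0.34) + 0.8416 × √(0.62 × 0.38 + 0.70 × 0.30)]² / 0.08²
= (1.3130 + 0.5618)² / 0.0064 = 549.2 per group.

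One-sided 5% with 80% power gives 433, and two-sided 5% with 90% power gives 735. Neither fits, so two-sided 5% and 80% is the likely basis. Then 549 / 8.8 = 62.4, reported as 62. The conversion therefore uses a design effect of exactly 1.

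**Step 2: patients needed once diagnoses are correlated.** Design effect DE = 1 + (m − 1) × ICC = 1 + 7.8 × ICC. Patients per period = 549 × DE / 8.8, rounded up.

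| Assumed ICC | DE | Problems per period | Patients per period |
|---|---|---|---|
| 0.05 | 1.39 | 763 | 87 |
| 0.10 | 1.78 | 977 | 112 |
| 0.20 | 2.56 | 1405 | 160 |
| 0.30 | 3.34 | 1834 | 209 |

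**Step 3: power of the possible intakes.** Effective n per period = patients × 8.8 / DE, entered in the same two-proportion test. For example, 100 patients at ICC 0.1 give 880 / 1.78 = 494 effective observations and 76% power.

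| Assumed ICC | 62 per period | 100 per period | 100 before, 200 after | 200 per period |
|---|---|---|---|---|
| 0.05 | 66% | 85% | 94% | 99% |
| 0.10 | 55% | 76% | 87% | 96% |
| 0.20 | 41% | 60% | 73% | 88% |
| 0.30 | 33% | 49% | 62% | 78% |

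Power stays at or above 80% up to an ICC of about 0.077 with 100 per period, about 0.15 with 100 before and 200 after, and about 0.28 with 200 per period.

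**Step 4: which intake applies.** Section 4 guarantees at least 4 weeks between a clinician's entry and switch-on, which is about 100 inpatients before. It also places the inpatient switch-on half-way through a four-month rotation, which could allow about 8 weeks, or 200 inpatients, on each side. The last three columns of the table cover this range.

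**Step 5: the outpatient statement.** 5 clinicians × 20 patients = 100 patients, the same number as the inpatient 4-week intake, justified by the same division. It too assumes independent entries within a patient.

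**Step 6: the definition of the proportion.** Section 4 forms a proportion for each patient and then aggregates. Sections 10.1 and 10.6.2 speak of the proportion of diagnoses, computed by team. If aggregating means averaging, each patient counts equally. If it means pooling, patients with more diagnoses count more. The two can differ when the number of diagnoses varies between patients, and section 10.3 is computed with the diagnosis as the unit.

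**The case against.** The strongest reply is that 62 is only a calculated minimum and nobody plans to stop there. The protocol expects 100 inpatients in 4 weeks and about 200 in 8, which absorbs a modest or even a sizeable ICC. This stands. A reader might infer from the design effect that the study is underpowered, but the documents do not support that: the ICC is unknown and the planned intake exceeds 62.

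The simple design effect may also overstate the loss. The comparison is made within teams, largely among the same rotation doctors before and after switch-on, so stable differences between teams largely cancel. This stands too, although correlation specific to the patient remains. In the other direction, the figures leave out any further clustering by team.

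A reader might also infer that the inpatient confidence intervals will be too narrow. If diagnoses were pooled as independent, the true standard error would be larger than the reported one by a factor of √DE: 1.18, 1.33 and 1.60 at ICC 0.05, 0.1 and 0.2. But section 10.6.2 gives no inpatient test, standard error or interval, section 4 works through per-patient proportions, and the method may be in an analysis plan that is not shown. An error in the planned intervals is not established.

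Finally, the rounding of 62.4 down to 62 is immaterial, and the mismatch between sections 4 and 10.6.2 is an ambiguity, since aggregating need not mean averaging.

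**Conclusion.** The point holds for the stated sample size. Section 10.3 obtains 62 patients by assuming zero correlation between diagnoses in the same patient, and that number falls short of the implied 80% power for any positive correlation. At assumed ICCs of 0.05 to 0.3 the requirement is 87 to 209 patients per period. Whether the study as planned reaches 80% power depends on the ICC and on the length of the period before switch-on, neither of which section 10.3 addresses. The figures rest on alpha and power inferred from the 549, a constant 8.8 diagnoses per patient, and an ICC range chosen for illustration. The statement that 5 outpatient clinicians suffice has the same fault, with little practical consequence because section 10.4 sets a minimum of 25. The definition of the inpatient proportion needs clarifying.

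**What to change.** - **Section 10.3, inpatients:** state alpha and power. Replace the single figure of 62 with patients per period over an assumed ICC range, showing the design effect. Add the power of the intake actually planned, for the guaranteed 4 weeks before switch-on and for 8 weeks.
- **Section 10.3, outpatients:** make the same correction to the 5-clinician statement.
- **Section 10.6.2:** keep the difference in proportions, stratified by team, and base its interval on the patient as the unit, for example by a bootstrap of patients within team and period. A mixed logistic model with a patient random intercept is a less direct choice: it gives a conditional odds ratio, which is not the stated outcome unless standardised back to a difference in proportions.
- **Sections 4 and 10.6.2:** use one definition of the inpatient proportion, either the mean of per-patient proportions or the pooled proportion of diagnoses.

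The cost is a few sentences, a small table and a less favourable stated figure. No additional patients or data are required.

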10.4 Planned recruitment rate

The target minimum sample sizes are as follows:

Clinicians for outpatient study: minimum 25, target 50

Clinicians for observation substudy: 5

Patient consultations for observation substudy (at least 2 pre and 2 post for each clinician, total 20)

Clinicians for inpatient study: minimum 25, target 50

Inpatient clinicians for interview: 5

The clinician participants will be recruited over a short period of time (a few weeks) via clinical meetings. As per the study timeline diagram, patient participants would be recruited from eligible clinics. As this is a qualitative study only a small sample is required (5 clinicians for each substudy for Feasibility study of 'MiADE' point of care natural language processing, EDGE number 157134, IRAS number 322887, Protocol, Version 1.1, DATE 24/07/2023 33/46

interview, and 2 outpatient consultations per clinician pre and post). Patients are seen on a single visit so there should be minimal loss to follow up, and clinicians will be easy to reach as they will most likely still be working at the Trust.

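### The 5-clinician outpatient requirement in section 10.3 comes from a two-proportion calculation that does not size a count endpoint; on that section's own inputs a Poisson comparison needs about 10

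*Protocol*

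**What the plan says.** Section 10.3 starts from a prior audit in which "62% of problem list entries were entered as structured data and there were mean 8.8 problems per patient". It sizes the inpatient comparison as follows: "In order to detect an increase from 62% to 70%, 549 problems are required in each group, which is 62 patients". It then turns to outpatients, "assuming each clinician sees 5 new patients each week, they will see 20 patients in a 4 week period", and concludes: "Using the same calculation as for inpatients, a sample size of only 5 clinicians is required to investigate the primary endpoint". The next sentence gives a larger target of 25 clinicians so that variability between clinicians can be assessed.

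Section 10.1 defines the outpatient primary outcome as "the difference in the mean number of structured problem list, medication or allergy entries", compared between periods with and without MiADE. Section 10.6.2 says that "multilevel Poisson regression will be used to calculate the ratio of counts of structured data entries between pre-MiADE and post-MiADE", with clinician as a random effect.

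On recruitment, section 10.4 states: "Clinicians for outpatient study: minimum 25, target 50". The study summary gives the same two numbers.

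**The concern.** The inpatient endpoint is a proportion: coded diagnoses supply a denominator, and each is either on the problem list or not. The outpatient primary endpoint has no such denominator. It is a crude number of entries per patient; manual review of notes as a reference standard belongs only to the observation substudy. A 62% to 70% calculation therefore sizes neither this endpoint nor the planned ratio of counts.

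The mismatch affects the variance. The binomial formula describes the count only if every patient has the same number of problems. In practice that number varies between patients and adds to the variance of the count. The calculation also allows for no difference in effect between clinicians, although section 10.6.2 expects to estimate one.

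What is at stake is how the sample size is read. If 5 is accepted as sufficient, 25 looks like a five-fold margin, and the protocol gives no valid statement of what effect the outpatient comparison could detect.

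**Working it through.** **Inputs.** From section 10.3: 62%, 70%, 8.8 problems per patient, 549 problems per group, 20 patients per clinician per 4 weeks. Alpha and power are not stated. Two-sided 0.05 and 80% power are inferred, because they reproduce 549.

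**1. The plan's own figure.** The pooled two-proportion formula without continuity correction gives n = [1.96 × √(2 × 0.66 × 0.34) + 0.8416 × √(0.62 × 0.38 + 0.70 × 0.30)]² / 0.08² = 549.2. The arcsine form gives 548.6. One-sided testing gives 433 and 90% power gives 735, so neither is what was used. Then 549 / 8.8 = 62.4 patients and 62.4 / 20 = 3.1, so 4 clinicians would meet the calculation. Five supply 100 patients (880 problems), at which this formula gives 94% power.

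**2. The same inputs as counts.** Mean entries before: 8.8 × 0.62 = 5.456. After: 8.8 × 0.70 = 6.16. Ratio = 1.129, log ratio = 0.1214. If every patient had exactly 8.8 problems, the variance before would be 8.8 × 0.62 × 0.38 = 2.07; as a Poisson count it is 5.456.

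**3. Poisson comparison, common effect, 4 weeks each side.** SE of the log ratio = √[1/(n × 5.456) + 1/(n × 6.16)].

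- 5 clinicians, n = 100 per period: SE = 0.0588, 0.1214 / 0.0588 = 2.064, power = Φ(2.064 − 1.96) = 54%. Simulation gives 54% to 55%.
- For 80% power: n = 7.849 × (1/5.456 + 1/6.16) / 0.1214² = 184.2 per period, and 184.2 / 20 = 9.2 clinicians. Nine give 79.1% and ten give 83.1%.

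**4. Dependence on the windows.** Section 4 gives at least 4 weeks between entry and switch-on, 8 weeks after switch-on and a prior 8-week period. The summary's estimate of 3000 outpatients is 25 × 5 × 24 weeks, and 24 − 8 − 8 = 8 weeks could remain for the pre-MiADE period.

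| Weeks pre / post | Patients pre / post, 5 clinicians | Power |
|---|---|---|
| 4 / 4 | 100 / 100 | 54% |
| 4 / 8 | 100 / 200 | 66% |
| 8 / 8 | 200 / 200 | 83% |

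With 4 and 8 weeks, 80% power needs 7.849 × [1/(20 × 5.456) + 1/(40 × 6.16)] / 0.1214² = 7.05, so 8 clinicians.

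**5. Dependence on the baseline mean.** The 8.8 counts problems only. The outpatient count adds medications and allergies, for which the protocol gives no figure. At the same ratio with 5 clinicians and 4-week windows, an assumed baseline of 4 entries gives 42% power and one of 10 entries gives about 80%.

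**6. The planned minimum of 25 clinicians.** With 4-week windows (500 patients per period), SE = 0.0263 and power is 99.6% under pure Poisson. At an assumed variance-to-mean ratio of 2 it is 90%, and at 3 it is 76%.

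**7. Allowing the effect to differ between clinicians.** Let τ be an assumed clinician SD of the log ratio. With 25 clinicians, 20 patients before and 40 after, and dispersion 2, SE = √{[τ² + 2 × (1/(20 × 5.456) + 1/(40 × 6.16))] / 25}. The ratio detectable with 80% power is exp(2.8016 × SE).

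| τ (assumed) | SE | Detectable ratio |
|---|---|---|
| 0.1 | 0.0382 | 1.11 |
| 0.2 | 0.0516 | 1.16 |
| 0.3 | 0.0682 | 1.21 |

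**The case against.** The protocol does not plan on 5 clinicians. It recruits at least 25, says the larger number is for assessing variability between clinicians, and estimates that variability in the analysis. This is also a feasibility study. The means 5.456 and 6.16 are not printed in the protocol; they are products of its figures. Longer windows or a higher baseline bring 5 clinicians to about 80% power or above. All of this stands, and it limits the consequence. It does not rescue the sentence, which rests on 4-week windows and on a formula that does not apply to a count.

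A reader might infer two stronger conclusions, and the documents support neither.

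- That the requirement is wrong by a factor of two or more whatever is assumed. It is not: with 8 weeks on each side, 5 clinicians reach 83% under pure Poisson, and with 4 and 8 weeks the requirement is 8.
- That 25 clinicians are too few. At dispersion 2 and τ of 0.2 or 0.3 the detectable ratio exceeds 1.129, but at τ = 0.1 it is 1.11 and does not. Neither dispersion nor τ has a source in the protocol, so these values show sensitivity and do not establish a shortfall.

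**Conclusion.** The 5-clinician requirement is unsupported as written, because the calculation behind it is for a different kind of endpoint. On section 10.3's own inputs, 5 clinicians give about 54% power, against 94% by the borrowed formula, and about 10 are needed for 80%.

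These figures assume 4-week windows, 8.8 problems as the basis of the count, two-sided 0.05 and 80% power, no overdispersion and one common effect. The first two could move the result either way; overdispersion or variation in effect between clinicians would raise the requirement.

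The defect is confined to the stated justification and the inconsistent target. The planned minimum of 25 is adequate under pure Poisson and remains at 90% at dispersion 2 with a common effect, so underpowering is not shown. The conflict between a target of 25 in section 10.3 and minimum 25, target 50 in section 10.4 and the summary needs no assumption.

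**What to change.** 1. Delete the 5-clinician sentence from section 10.3.
2. State instead the ratio of mean structured entries detectable with 80% power at the minimum of 25 clinicians. Use the actual pre and post windows, state alpha and sidedness, and show a labelled range of assumed baseline mean (including medications and allergies), dispersion and clinician SD of the log ratio. The table in step 7 of the working shows the form.
3. Use one recruitment statement in section 10.3, section 10.4 and the summary.

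The cost is protocol wording and a short calculation. The stated position becomes less favourable than the 5-clinician claim, but no extra enrolment is needed, since 25 to 50 clinicians are already planned.
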